## **7. PLANNED ANALYSIS**

For End-Of-Text (EoT) tables, the set of summary statistics is: N / Mean / SD / Min / Q1 / Median / Q3 / Max.

For tables that are provided for endpoints with some extreme data, median, quartiles and percentiles should be preferred to mean, standard deviation, minimum and maximum.

Tabulations of frequencies for categorical data will include all possible categories except AE analysis and will display the number of observations in a category as well as the percentage (%) relative to the respective treatment group (unless otherwise specified, all patients in the respective patient set whether they have non-missing values or not). Percentages will be rounded to two decimal places. The category missing will be displayed only if there are actually missing values.

In addition, individual values on demographics, safety and effectiveness will be presented in subject data listings.

### **7.1 DEMOGRAPHIC AND OTHER BASELINE CHARACTERISTICS**

Only descriptive statistics are planned for this section of the report.

### **7.2 CONCOMITANT DISEASES AND MEDICATION**

Concomitant diseases will be coded by the latest version of Medical Dictionary for Regulatory Activities (MedDRA). Frequency of patients will be summarised by system organ class (SOC) and preferred term (PT).

Concomitant medication will be coded by latest version of “Nihon-iyakuhinshu”.

### **7.3 TREATMENT COMPLIANCE**

Compliance data is not collected in this study.

### **7.4 PRIMARY ENDPOINT(S)**

The analysis of the primary endpoint is described in [Section 7.8.1](#).

**7.5 SECONDARY ENDPOINT(S)**

**7.5.1 Key secondary endpoint(s)**

This section is not applicable as no key secondary endpoint has been specified in the protocol.

**7.5.2 (Other) Secondary endpoint(s)**

Effectiveness at each visit in each patient is determined based on the change of asthma control status from baseline. See the assessment table for effectiveness and the NIS Protocol Section 9.3.2.2: 1.

Table 7.5.2: 1 Assessment table for effectiveness

Baseline \ After administration	Well controlled	Insufficiently-controlled	Poorly-controlled	Unknown / Missing
Well controlled	No change	Improvement	Improvement	Unknown
Insufficiently-controlled	Worse	Worse	Improvement	Unknown
Poorly-controlled	Worse	Worse	Worse	Unknown
Unknown / Missing	Unknown	Unknown	Unknown	Unknown

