Tiotropium delivered via the Respimat® inhaler once daily also demonstrated long-term safety and tolerability compared with that of placebo when administered at a daily dose of 2.5 and 5 µg to adult patients with asthma. Exposure to tiotropium in the clinical program covered more than 1000 patient-years in more than 2200 patients. The overall frequencies of AEs, drug-related AEs, and SAEs were similar across all treatment dose groups in trials with the same duration and patient population. In general, no specific concerns with regard to abnormal vital signs were raised for patients who took tiotropium. There were no patterns of increased particular AEs for the tiotropium treatment groups compared with that of placebo in any subgroup analysis. No deaths were reported during the entire clinical program. According to the current guidelines for the treatment of asthma, although various treatment options are available for long-term asthma management including ICS as the first-line therapy and other additional therapies depending on asthma severity (e.g., LABA, leukotriene receptor antagonist, theophyllines, antihistamines, oral steroids, anti-IgE), improvement of symptoms is insufficient in many patients (i.e., uncontrolled and/or at potential risk of asthma exacerbation), and there is a growing medical need for additional therapeutic options for the treatment of asthma. Responding to the medical needs, inhaled administration of anticholinergic bronchodilator tiotropium is a new additional maintenance therapy in patients with asthma who remain symptomatic despite treatment with at least ICS. Treatment with tiotropium improves lung function and symptoms of asthma patients more appropriately and may be an important paradigm shift in the treatment of asthma patients.

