#### 9.3.2.2 Secondary outcome

- Change from baseline in asthma control status at Week 12

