#### 9.3.2.2: 1 Asthma control status Table

Patients control status	Well-controlled	Insufficiently-controlled	Poorly-controlled
	Meet all the criteria	Meet 1 or 2 criteria	Meet all of 3 Criteria
Asthma symptoms (in the daytime or at night)	None	Once or more a week	Once or more a week
Use of reliever	None	Once or more a week	Once or more a week
Limitation of activities, including exercise	None	Restricted	Restricted

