#### **4. CHANGES IN THE PLANNED ANALYSIS OF THE STUDY**

No change has been made in the planned analyses from the statistical methods described in the NIS Protocol.

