#### **5.2.2 Secondary endpoint(s)**

The secondary endpoints will be used as defined in the NIS Protocol Section 9.3.2.2.

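### SAP Table 7.5.2: 1 codes patients whose asthma control is unchanged but not well controlled as Worse, which overstates worsening on the protocol's only listed secondary outcome

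*SAP*

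**What the plan says.** Protocol section 9.3.2.2 lists one secondary outcome: "Change from baseline in asthma control status at Week 12". Protocol table 9.3.2.2: 1 defines three ordered states from three criteria (symptoms, reliever use, limitation of activities). Well-controlled requires that none is present, insufficiently-controlled is "Meet 1 or 2 criteria", and poorly-controlled means all three.

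SAP section 5.2.2 adopts this outcome: "The secondary endpoints will be used as defined in the NIS Protocol Section 9.3.2.2". SAP section 7.5.2 gives the classification rule: "Effectiveness at each visit in each patient is determined based on the change of asthma control status from baseline". Table 7.5.2: 1 then assigns a label to each pair of states. Its first row gives No change to Well/Well and Improvement to the other two known-status cells. The next two rows read "Insufficiently-controlled Worse Worse Improvement Unknown" and "Poorly-controlled Worse Worse Worse Unknown".

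**The concern.** Under a rule based on change from baseline, a patient in the same state before and after treatment has not changed. The table applies this to Well/Well only. Insufficiently/Insufficiently and Poorly/Poorly, where the state is equally unchanged, are coded Worse. No Change can therefore be reached only by patients who were well controlled at both times, and nothing in the available text says that remaining uncontrolled is to count as deterioration.

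The affected group may be large. Protocol section 7 positions the drug for "patients with asthma who remain symptomatic despite treatment with at least ICS", whereas well-controlled status requires no symptoms, no reliever use and no limitation. Programmed as written, every patient who stays insufficiently or poorly controlled would be reported as having deteriorated, at Week 4 and at Week 12. In a descriptive study the category frequencies are the result, and protocol section 12 sends the reports to the regulator and plans a publication.

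**Working it through.** **Step 1. Compare the table with its stated rule.** The rule is: better state = Improvement, same state = No change, poorer state = Worse. There are nine cells in which both states are known. With columns as baseline and rows as after administration:

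| After \ Baseline | Well | Insufficiently | Poorly |
|---|---|---|---|
| Well | No change (agrees) | Improvement (agrees) | Improvement (agrees) |
| Insufficiently | Worse (agrees) | **Worse (rule: No change)** | Improvement (agrees) |
| Poorly | Worse (agrees) | Worse (agrees) | **Worse (rule: No change)** |

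Seven of nine cells agree, and the two failures are the diagonal cells in question. The table has 3 Improvement, 1 No change and 5 Worse; the rule gives 3, 3 and 3.

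With rows as baseline, only Well/Well agrees (1 of 9), and a move from well to poorly controlled would be an Improvement. Columns as baseline is therefore plainly the intended reading. Transposing the table leaves the diagonal in place, so the two cells are wrong on either reading.

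**Step 2. Size of the error.** Let s = P(insufficient at baseline) × P(stays insufficient) + P(poor at baseline) × P(stays poor). With columns as baseline:

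- reported Worse = true Worse + s
- reported No change = true No change − s
- reported Improvement = true Improvement

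The error is zero only if s = 0. For scale, with the protocol's planned safety set of 150, s = 10%, 30% or 50% moves 15, 45 or 75 patients.

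**Step 3. Scenarios.** The documents give neither the baseline mix nor the transition rates, so every input here is an assumption. Each triple is well/insufficient/poor, in percent.

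| Scenario | Baseline | From well | From insufficient | From poor |
|---|---|---|---|---|
| Low | 30/55/15 | 90/8/2 | 55/42/3 | 25/50/25 |
| Middle | 10/60/30 | 90/8/2 | 45/50/5 | 15/45/40 |
| High | 5/55/40 | 85/12/3 | 25/67/8 | 8/32/60 |

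- Low: s = 55 × 0.42 + 15 × 0.25 = 23.1 + 3.75 = 26.85 points. True Worse = 30 × 0.10 + 55 × 0.03 = 4.65%. Reported Worse = 4.65 + 26.85 = 31.5%.
- Middle: s = 60 × 0.50 + 30 × 0.40 = 30 + 12 = 42 points. True Worse = 10 × 0.10 + 60 × 0.05 = 4%. Reported Worse = 46%.
- High: s = 55 × 0.67 + 40 × 0.60 = 36.85 + 24 = 60.85 points. True Worse = 5 × 0.15 + 55 × 0.08 = 5.15%. Reported Worse = 66.0%.

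| Scenario | Improvement / No change / Worse by the rule | As the SAP codes it |
|---|---|---|
| Low | 41.5 / 53.9 / 4.7% | 41.5 / 27.0 / 31.5% |
| Middle | 45 / 51 / 4% | 45 / 9 / 46% |
| High | 29.8 / 65.1 / 5.2% | 29.8 / 4.3 / 66.0% |

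Figures are rounded and may not sum to exactly 100. A separate assumed mix (baseline 5/60/35, with stability varied from low to high) gives the same picture: Worse is 7.0% by the rule and 39.8% to 76.5% as coded.

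**The case against.** The strongest defence is that the pattern is deliberate. Both not-well-controlled diagonal cells carry the same label, and the table is titled as an assessment of effectiveness, so the sponsor may regard staying uncontrolled on treatment as unfavourable. The public SAP has gaps in its section numbering, so a supporting definition could sit in text that is not available. This is possible, but it does not rescue the label. The governing sentence defines the category by change from baseline, and merging persistence with real deterioration under Worse hides both.

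Some lesser points stand:

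- SAP section 4 says that "No change has been made in the planned analyses from the statistical methods described in the NIS Protocol". The protocol gives no scheme for classifying change, so adding one does not strictly contradict that statement. It shows only that no departure was declared.
- A patient who goes from two criteria to one stays insufficiently controlled and is coded Worse despite meeting fewer criteria. This shows how badly the label fits, but the three-level scale would miss the gain even after the correction.
- Control status is collected only if available, and SAP section 7 by default takes percentages over all patients in the set. If a fraction u is Unknown, the scenario shifts shrink by the factor 1 − u. The identity in s still holds when s is taken over the same denominator.
- The figure of 150 is the safety set. The effectiveness set is a subset whose size is not stated.
- The analysis is secondary and descriptive, and individual values will be listed, so the split could be rebuilt. Listings do not, however, correct a mislabelled summary.

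**Conclusion.** The concern holds. Two of the nine known-status cells in SAP Table 7.5.2: 1 contradict the rule stated directly above them, on either reading of the axes. Worse is overstated, and No change understated, by exactly the share of patients who remain insufficiently or poorly controlled. Under the assumed scenarios Worse goes from about 4–5% to about 32–66%. That range illustrates the effect and is not a forecast, since the documents do not supply the inputs.

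The Improvement proportion (with columns as baseline), the primary adverse drug reaction outcome and the study size are not affected. For a descriptive secondary table this is at the lower end of what must be corrected. It still belongs there, because following the SAP exactly would report unchanged patients as deteriorated on the only secondary outcome the protocol lists.

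**What to change.** Set all three diagonal cells of Table 7.5.2: 1 to No change. If the sponsor wants to flag patients who stay uncontrolled, give them their own category, such as *Unchanged, not well controlled*, and keep it out of Worse. Reporting the full baseline-by-visit shift table alongside would let readers see every transition.

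Check the two cells and the axis orientation against the original PDF and the derivation code, then label the axes so that columns are unmistakably baseline and rows after administration. The corner label may have been disturbed in PDF extraction, so this is a check and not a claimed error.

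The cost is two cells and the axis labels in one SAP table, plus the matching derivation code. No new data are needed.

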#### **9.2.2 Study population**

##### **9.2.2.1 Inclusion/Exclusion criteria**

###### Inclusion criteria:

- Patients diagnosed with mild to moderate persistent bronchial asthma
- Patient aged  $\geq 15$  years
- Patients who are naive to Spiriva Respimat and receive Spiriva Respimat for the first time for treatment of bronchial asthma on top of at least ICS treatment.

\*:Asthma severity is defined by “Table 6 Classification of asthma severity based on the present treatment (adult)” of “Japanese Guideline for Adult Asthma 2014”[[P14-15105](#)].

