###### Exclusion criteria:

- Patients who have a contraindication to Spiriva Respimat defined in the package insert for Spiriva Respimat
- Patients who have been enrolled in this study before.

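### Percent improved in asthma control depends on how many patients were already well controlled at baseline, and the SAP's scoring table must be reconciled before it can be reported

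*SAP*

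**What the plan says.** Protocol 9.3.2.2 names one secondary outcome, "Change from baseline in asthma control status at Week 12". It is the only effectiveness outcome the protocol names. Table 9.3.2.2: 1 grades control on three items (symptoms, reliever use, limitation of activities). Well controlled means none on all three, and no category lies above it.

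The rationale in Protocol 7 says that tiotropium "is a new additional maintenance therapy in patients with asthma who remain symptomatic despite treatment with at least ICS". The entry criteria in Protocol 9.2.2.1 are wider. They take "Patients diagnosed with mild to moderate persistent bronchial asthma", aged 15 or over, who "receive Spiriva Respimat for the first time for treatment of bronchial asthma on top of at least ICS treatment". A footnote defines severity by present treatment. Apart from contraindications, the only exclusion is "Patients who have been enrolled in this study before". None of these refers to current control.

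SAP 6.3 builds the effectiveness set from safety-set patients with a baseline value and at least one on-treatment value of any of five measures, again with no condition on baseline control. SAP 7.5.2 gives the scoring rule: "Effectiveness at each visit in each patient is determined based on the change of asthma control status from baseline". SAP 7 sets the default denominator for percentages of categorical data as everyone in the set, including patients with missing values. SAP 6.6 does not impute missing effectiveness data.

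**The concern.** A patient at the top of the scale has complete data but no room to improve. If such patients are counted in the denominator, percent improved reflects the baseline case mix as well as what happened on treatment. The study has no comparator, so this percentage is itself the effectiveness result. Effectiveness is part of the stated objective (Protocol 8), interim results go into the re-examination documents, and publication is planned (Protocol 12).

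The case mix comes from about 25 sites chosen partly because they monitor peak flow routinely (Protocol 9.2.1). A reader could not tell whether a modest percentage means little benefit or many patients who were well controlled from the start. Nor would it show how often control improved in the symptomatic patients the rationale describes.

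**Working it through.** The documents give no expected percent improved, no power for effectiveness and no well-controlled share, so there is no planned figure to reproduce.

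**Step 1: read the scoring table both ways.** The corner cell of Table 7.5.2: 1 names baseline first and after administration second, which normally means rows = baseline.

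| Baseline to follow-up | Rows = baseline (as labelled) | Columns = baseline |
|---|---|---|
| Well to well | No change | No change |
| Well to insufficient | Improvement | Worse |
| Well to poor | Improvement | Worse |
| Insufficient to well | Worse | Improvement |
| Insufficient to insufficient | Worse | Worse |
| Insufficient to poor | Improvement | Worse |
| Poor to well | Worse | Improvement |
| Poor to insufficient | Worse | Improvement |
| Poor to poor | Worse | Worse |

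As labelled, loss of control is an improvement and gain of control is a worsening. Only columns = baseline gives the right direction. The two unchanged cells scored as worse lie on the diagonal, so they do not depend on the axis label.

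**Step 2: the ceiling.** With columns = baseline, a patient well controlled at baseline can score only 'No change', 'Worse' or 'Unknown'.

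**Step 3: the effect on the percentage.** Let p be the proportion improving among patients not well controlled at baseline, w the share well controlled at baseline, and u the share scored 'Unknown' (taken as equal across baseline groups). With everyone in the set as denominator:

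percent improved = p × (1 − w) × (1 − u)

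With p = 50% (assumed) and u = 0:

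| w (assumed) | Calculation | Percent improved |
|---|---|---|
| 5% | 0.50 × 0.95 | 47.5% |
| 10% | 0.50 × 0.90 | 45% |
| 20% | 0.50 × 0.80 | 40% |
| 40% | 0.50 × 0.60 | 30% |

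With w = 20% and u = 20%, the result is 0.50 × 0.80 × 0.80 = 32%. Restricted to patients not well controlled at baseline with known status, it is p = 50% in every case.

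**Step 4: compare with the axis problem.** Assume a baseline mix of 20% well, 50% insufficient and 30% poor. Assume follow-up distributions (well/insufficient/poor) of 90/10/0%, 50/40/10% and 30/40/30% respectively.

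- Columns = baseline: improvement 0.50 × 0.50 + 0.30 × 0.70 = 46%; no change 0.20 × 0.90 = 18%; worse 36%.
- Among patients not well controlled at baseline: 46 / 80 = 57.5% improved.
- Rows = baseline, same data: improvement 0.20 × 0.10 + 0.50 × 0.10 = 7%; no change 18%; worse 75%.

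In this example the ceiling costs 57.5 − 46 = 11.5 points, and the axis reading moves the result by 46 − 7 = 39 points. Correcting the diagonal moves 0.50 × 0.40 + 0.30 × 0.30 = 29% of patients from 'Worse' to 'No change'.

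**The case against.** The strongest reply has four parts.

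- **The table as labelled does not show a ceiling.** A reader might infer that the plan never lets a well-controlled patient score an improvement. The printed label contradicts this: with rows = baseline, the well-controlled row holds two improvement cells. The ceiling follows only when columns are baseline. This part stands, so reconciliation has to come first.
- **SAP 7.5.2 names no overall percent improved.** It defines a classification per patient and visit. The pooled percentage is inferred from the general denominator rule in SAP 7. The public SAP also does not show Sections 5.3, 6.4 and 7.6, and SAP 7.8.1 points to subgroups defined in 6.4. It cannot be concluded that the plan has no display by baseline status, only that 7.5.2 specifies none.
- **The well-controlled share may be small.** The rationale describes patients who remain symptomatic on ICS. At shares of 5% to 10%, the loss in the example is 2.5 to 5 points. It is tempting to say that the same effect could read anywhere from 20% to 50%, but the lower end needs 60% well controlled at baseline, which nothing in the documents supports.
- **The outcome is descriptive.** Protocol 9.3.2.1 sets no primary effectiveness outcome, Protocol 9.7 foresees no confirmatory testing, and Protocol 9.9 already acknowledges selection of sites. An all-user description also fits the stated objective. This limits the consequence, but a single-arm percentage still needs a stated denominator.

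A reader might also infer that 'No change' mixes maintained control with persistent lack of control. As printed it does not: it covers only well to well. The mixing would appear once the diagonal is corrected, which is a reason to report within baseline status.

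**Conclusion.** The point holds in a limited form. Entry and the effectiveness set admit patients already at the top of the control scale. On the only clinically coherent reading of Table 7.5.2: 1, an all-patient percent improved equals the rate among patients with room to improve, multiplied by (1 − w) and again by (1 − u). The size is unknown because no document gives w, and p = 50% is an illustration. The rationale suggests w may be modest.

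The larger defect is in the table itself: label and cells disagree in direction, and unchanged insufficiently or poorly controlled patients are scored as worse. The direction problem could be an artefact of PDF extraction and should be checked in the original. The diagonal scoring does not depend on the axis label. Nothing here biases a test. What is at stake is whether the only named effectiveness outcome can be interpreted.

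**What to change.** In SAP 7.5.2:

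1. Check the axis label against the original, correct the axes if they are wrong there, and correct the two unchanged cells (insufficient to insufficient, poor to poor).
2. Present the Week 12 result as a baseline-by-Week 12 shift table with percentages within each baseline status.
3. Report percent improved among patients insufficiently or poorly controlled at baseline with known Week 12 status.
4. Report separately the percentage remaining well controlled among those well controlled at baseline.
5. Show the number with unknown status beside each figure.

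This changes SAP wording and one table layout. It uses data already collected and changes nothing at the sites or in who is enrolled. The cost is a smaller denominator, and so less precision, for percent improved.

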**7.7 EXTENT OF EXPOSURE**

Only descriptive statistics are planned for this section of the report.

**7.8 SAFETY ANALYSIS**

All safety analyses will be performed on the safety set.

### 7.8.1 Adverse events

Unless otherwise specified, the analyses of adverse events will be descriptive in nature. All analyses of AEs will be based on the number of patients with AEs and NOT on the number of AEs.

Furthermore, for analysis of AE attributes such as duration, severity, etc. multiple AE occurrence data on the CRF, will be collapsed into AE episodes provided that all of the following applies:

- The same MedDRA lowest level term was reported for the occurrences
- The occurrences were time-overlapping or time-adjacent (time-adjacency of 2 occurrences is given if the second occurrence started on the same day or on the day after the end of the first occurrence)
- Treatment did not change between the onset of the occurrences OR treatment changed between the onset of the occurrences, but no deterioration was observed for the later occurrence

For further details on summarization of AE data, please refer ([3](#), [4](#))

AE analyses will be carried out after integrating AE data from CRF and AE data from perceive system.

In addition, AEs coded as “no adverse event” will not be included in the AE analyses.

The analysis of adverse events will be based on the concept of treatment emergent adverse events. All adverse events will be analysed up to last drug intake + 30 days. For details on the treatment definition, see [Section 6.1](#).

An overall summary of adverse events will be presented.

The frequency of patients with AEs, ADRs will be summarised by primary system organ class and preferred term. Also, the frequency of patients with ADRs will be summarised by primary system organ class, preferred term and the time to first onset date (<29, 29 to <57, 57 to <85, >=85 days). Separate tables will be provided for patients with ADRs stratified by various patient subgroups defined in [Section 6.4](#), for patients with serious AEs. Subgroup analysis will display the frequency of patients, percentage (%) and odds ratio with 95%CI. Logistic regression will be used for odds ratio. The ‘unknown’ and ‘missing’ categories are excluded to calculate odds ratio. Patients with ‘priority survey items’ according to the drug’s Risk Management Plan (RMP) will be summarised separately.

An ADR is defined as an AE for which either the investigator or the sponsor (or both) assess the causal relationship to Spiriva Respimat either as “Possibility high”, “Possibility low” or “Unknown”. The system organ classes will be sorted according to the standard sort order specified by EMA, preferred terms will be sorted by frequency (within system organ class).

A serious AE is defined as an AE for which either the investigator or the sponsor (or both) assess the seriousness either as “Serious”.

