### 9.3.2 Outcomes

#### 9.3.2.1 Primary outcome

The primary Outcome is the absolute and relative (%) frequency of patients with suspected adverse drug reactions (ADRs).

Safety will be assessed by use of the following other parameters of interest:

- Adverse events irrespective of seriousness
- Laboratory tests (if corresponding AEs are reported)

There is no primary outcome for effectiveness as the primary objective of a PMS is evaluating safety.

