### **9.7.1 Main analysis**

The analysis of outcome events will include all patients registered in the study and receiving the Spiriva Respimat treatment. All outcome events are based on reported AE data which will be handled according to BI standards.

The safety analysis will include all patients registered in the study and receiving the Spiriva Respimat treatment. In general, safety analyses will be descriptive in nature, will be based on BI standards, and will focus on ADRs related to the Spiriva Respimat treatment.

AEs will be coded using the current version of the Medical Dictionary for Regulatory Activities (MedDRA) and will be based on the concept of treatment emergent AEs. To this end, all AEs occurring between the first intake of Spiriva Respimat prescribed at baseline visit and within 30 days (inclusive) after the last intake will be considered 'treatment emergent'. An AE is considered to be ADR if either the physician who has reported the AE or the sponsor assesses its causal relationship as 'related'.

The frequency of AEs/ADRs will be tabulated by system organ class and preferred term for overall and for subgroups based on the important baseline characteristics.

No imputation is planned for missing AE data except for missing onset dates which will be handled according to BI standard.

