### Collection of AEs

The study design is of non-interventional nature and the study is conducted within the conditions of the approved marketing authorisation. Sufficient data from controlled interventional trials are available to support the evidence on the safety and efficacy of the studied BI drug. For this reason the following AE collection and reporting requirements have been defined.

The following must be collected by the investigator in the eCRF. When any adverse events occur, the data should be immediately entered into eCRF and transmitted. :

- all adverse drug reaction (ADRs) (serious and non-serious),
- all AEs with fatal outcome,

All ADRs, including those persisting after study completion must be followed up until they are resolved, have been sufficiently characterized, or no further information can be obtained.

The investigator carefully assesses whether an AE constitutes an ADR using the information below.

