### Causal relationship of adverse event

The definition of an adverse reaction implies at least a reasonable possibility of a causal relationship between a suspected medicinal product and an adverse event. An adverse reaction, in contrast to an adverse event, is characterised by the fact that a causal relationship between a medicinal product and an occurrence is suspected.

Medical judgment should be used to determine the relationship, considering all relevant factors, including pattern of reaction, temporal relationship, de-challenge or re-challenge, confounding factors such as concomitant medication, concomitant diseases and relevant history.

Arguments that may suggest **a reasonable causal relationship** could be:

- The event is **consistent with the known pharmacology** of the drug
- The event is known to be caused by or **attributed to the drug class**.
- A **plausible time to onset of the event** relative to the time of drug exposure.
- Evidence that the **event is reproducible** when the drug is re-introduced

- **No medically sound alternative etiologies** that could explain the event (e.g. preexisting or concomitant diseases, or co-medications).
- The event is typically **drug-related and infrequent in the general population** not exposed to drugs (e.g. Stevens-Johnson syndrome).
- An indication of dose-response (i.e. greater effect size if the dose is increased, smaller effect size if dose is diminished).

Arguments that may suggest that there is **no reasonable possibility of a causal relationship** could be:

- No plausible time to onset of the event relative to the time of drug exposure is evident (e.g. pre-treatment cases, diagnosis of cancer or chronic disease within days/weeks of drug administration; an allergic reaction weeks after discontinuation of the drug concerned)
- Continuation of the event despite the withdrawal of the medication, taking into account the pharmacological properties of the compound (e.g. after 5 half-lives). Of note, this criterion may not be applicable to events whose time course is prolonged despite removing the original trigger.
- Additional arguments amongst those stated before, like alternative explanation (e.g. situations where other drugs or underlying diseases appear to provide a more likely explanation for the observed event than the drug concerned).
- Disappearance of the event even though the study drug treatment continues or remains unchanged.

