## **5. ENDPOINT(S)**

### **5.1 PRIMARY ENDPOINT(S)**

The primary endpoints will be used as defined in the NIS Protocol Section 9.3.2.1.

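### Does the SAP widen the primary ADR definition by counting AEs of unknown causality?

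*SAP*

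**What the plan says.** Protocol 9.3.2.1 sets the primary outcome: "The primary Outcome is the absolute and relative (%) frequency of patients with suspected adverse drug reactions (ADRs". SAP 5.1 takes it over without alteration ("The primary endpoints will be used as defined in the NIS Protocol Section 9.3.2.1"), and SAP 7.4 refers its analysis to SAP 7.8.1.

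The rule for calling an AE an ADR appears twice:

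- **Protocol 9.7.1:** an AE qualifies if the reporting physician "or the sponsor assesses its causal relationship as 'related".
- **SAP 7.8.1:** an AE qualifies if the investigator, the sponsor or both assess "the causal relationship to Spiriva Respimat either as “Possibility high”, “Possibility low” or “Unknown".

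The protocol's causality guidance (Section 11.2) says that an adverse reaction, unlike an adverse event, is "characterised by the fact that a causal relationship between a medicinal product and an occurrence is suspected". SAP Section 4 states: "No change has been made in the planned analyses from the statistical methods described in the NIS Protocol".

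**The concern.** The two rules agree that either assessor is enough. They differ in the words for causality: the protocol has the single word 'related', and the SAP has three grades, one of which is 'Unknown'. Taken literally, an event whose causality nobody could judge is not the same as one judged related. If the SAP rule is wider than the protocol's, it can only keep or raise the numerator of the sole primary outcome, and SAP Section 4 would be wrong to declare no change.

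The same definition feeds the ADR tables by system organ class and preferred term, the tables by time to onset and the subgroup odds ratios. A reader holding only the protocol would take the reported percentage as patients with an AE judged related. That reader could not tell from the summary table how much of it came from 'Unknown' alone.

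**Working it through.** **1. Do the texts conflict?**

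| Element | Protocol | SAP |
|---|---|---|
| Who decides | physician or sponsor (9.7.1) | investigator, sponsor or both (7.8.1) |
| Outcome wording | suspected ADRs (9.3.2.1) | adopts 9.3.2.1 (5.1) |
| Causality wording | 'related' (9.7.1); at least a reasonable possibility (11.1); suspected (11.2) | two 'possibility' grades and 'Unknown' (7.8.1) |
| Causality scale | none given | three qualifying grades |

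With no scale in the protocol, 'related' there is an ordinary word and not one box on a form. It has to be turned into recorded grades somewhere, and SAP Section 3 says that supplying such technical detail is the SAP's purpose. SAP 5.1 also ties the primary endpoint to Protocol 9.3.2.1, where the word is 'suspected'. Placing 'Unknown' on the suspected side is compatible with that. The visible SAP is the revision of 19 October 2018, before the planned end of data collection on 31 December 2018 (Protocol Section 6), so the rule was written down in advance.

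**2. When would the two rules give different results?** Both conditions must hold:

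- (a) 'related' is meant to cover only the two 'possibility' grades. No passage says so.
- (b) At least one patient has an AE graded 'Unknown' and no AE in a higher grade.

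If either fails, the two frequencies are identical.

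**3. How likely is (b)?** Protocol 11.2 requires the investigator to enter "all adverse drug reaction (ADRs) (serious and non-serious") and AEs with fatal outcome. An event entered under the first heading has already been judged an ADR. On the second, Protocol Section 7 reports "No deaths were reported during the entire clinical program". Few 'Unknown'-only patients are therefore to be expected. Zero is not established: Protocol 9.3.2.1 and 9.3.3 list adverse events in general, and SAP 7.8.1 merges in AE data from a second system.

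**4. Size if both conditions hold.** The plan's own figure is a safety set of 150, with 180 enrolled (Protocol 9.5). No formula is given. It is consistent with an assumed 95% chance of seeing at least one case at the protocol's rate of about 2.0%: ln(0.05)/ln(0.98) gives n = 149. At the 1.8% quoted for each main ADR, n would be 165. The figure of 150 is not in dispute and serves here only as the denominator.

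Each patient counted only through 'Unknown' adds:

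- 1/150 = 0.67 percentage points
- 1/180 = 0.56 points, if all enrolled patients enter the safety set

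The documents do not give the share p of such patients. For an assumed range at n = 150, with expected number 150p and chance of at least one 1 − (1 − p)^150:

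| Assumed p | Expected patients | Added points | Chance of at least one |
|---|---|---|---|
| 0% | 0 | 0 | 0% |
| 0.5% | 0.75 | 0.5 | 53% |
| 1% | 1.5 | 1.0 | 78% |
| 2% | 3 | 2.0 | 95% |

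**5. Size against the precision of the study.** Assume 3 of 150 patients have an AE judged related. The intervals are exact Clopper-Pearson, an assumption because the protocol names no method:

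| 'Unknown'-only patients added | Frequency | 95% CI |
|---|---|---|
| 0 | 2.00% | 0.41 to 5.73 |
| 1 | 2.67% | 0.73 to 6.69 |
| 2 | 3.33% | 1.09 to 7.61 |
| 3 | 4.00% | 1.48 to 8.50 |
| 5 | 5.33% | 2.33 to 10.24 |

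Even with five added patients, the estimate of 5.33% stays inside the interval around the unaltered 2.00% (upper limit 5.73%).

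**The case for a change.** The strongest case for acting is that in a descriptive study the reported frequency is itself the result, so its case definition should be traceable from protocol to SAP. Three main ADRs at 1.8% each mean about 2.7 patients each in 150 (150 × 0.018), so one or two added patients would be visible. The SAP would hardly list 'Unknown' if that grade never occurred. The remedy would be a sentence and one table row from data already coded.

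Part of this stands. No visible text says that 'Unknown' falls within 'related', and a cross-reference in SAP 7.8.1, or a citation of the company standard if it holds the mapping, would be good housekeeping. The rest is weaker:

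- Listing a grade shows that the scale contains it, not that patients would qualify through it alone.
- The instruction in Protocol 9.4 to enter any adverse event at once recurs in Protocol 11.2 directly before the list limited to ADRs and fatal AEs. It can be read as a rule about timing and not as wider collection.
- Protocol 9.7.1 relies on company standards for AE handling, and some SAP text is not public. A missing mapping in the visible pages is thin evidence that none exists.
- SAP Section 7 provides subject listings of individual safety values. With about 150 patients, 'Unknown'-only cases could be counted there if causality is listed; the columns are not specified.
- An extra row would put a second ADR percentage beside the primary one without changing it.

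**Conclusion.** The difference in wording is real, but the primary analysis can run as written. SAP 7.8.1 gives a usable and cautious working definition of a term that the protocol left without a scale, and it fits the protocol's outcome of suspected ADRs. That the SAP rule is wider than the protocol's is an assumption and is not stated in either document.

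If the assumption were true, the effect would be 0.67 percentage points per affected patient at n = 150, with the number of such patients unknown and possibly zero. Protocol 9.7 foresees no confirmatory testing, so no decision depends on it. This rests on reading 'related' together with 'suspected', and on the visible text alone. What remains is an optional sentence for traceability.
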